## 1. Protocol Summary

### 1.1. Synopsis

**Protocol Title:** CoolSculpting® Elite: Multi-Country Study to Evaluate Patient Satisfaction for Non-Invasive Fat Reduction in Abdomen, Flanks, Upper Arms, Inner Thighs, Outer Thighs and Submental Area [REDACTED]

**Short Title:** CoolSculpting Elite for Non-Invasive Fat Reduction

**Rationale:** The purpose of this trial is to further evaluate the safety, effectiveness, and patient satisfaction with the redesigned dual applicator CoolSculpting Elite System when cryolipolysis treatments are applied simultaneously or sequentially for non-invasive subcutaneous fat reduction of the abdomen and flanks, upper arms, submental area, inner thighs, and/or outer thighs. In addition, patient reported outcome (PRO) instruments were developed to better assess overall patient satisfaction.

### Objectives and Measures

Objectives	Measures
To evaluate participant satisfaction and effectiveness of the CoolSculpting Elite System using CoolSculpting Elite applicators for non-invasive subcutaneous fat reduction of the abdomen and flanks, upper arms, inner thighs, outer thighs and submental area	

• Cryolipolysis Satisfaction Questionnaire (CSQ)-Midsection (abdomen and flanks)

• CSQ-Overall (if additional body area(s) beyond abdomen and flanks are treated)

• CSQ for individual additional body areas treated (upper arms, inner thighs, outer thighs, submental area)

• Cryolipolysis General Procedure Questionnaire (CGPQ)

• Cryolipolysis Psychosocial Impact Questionnaire (CPIQ)

• Participant Evaluation of Noticeable Improvement

• Photography and independent photography review (IPR)

• 3D (three-dimensional) imaging of change in volume of fat

To evaluate safety of the CoolSculpting Elite System using CoolSculpting Elite applicators for non-invasive subcutaneous fat reduction of the abdomen and flanks, upper arms, inner thighs, outer thighs and submental area	

• Adverse events (AEs) and adverse device effects (ADEs); serious adverse events (SAEs), serious adverse device effects (SADEs)

• Unanticipated AEs or SAEs (previously unknown to the device)

• Pain assessment

## Overall Design

**Disclosure Statement:** This is a multicenter, multi-country, prospective, open-label, nonrandomized, interventional cohort, medical device post-marketing study evaluating the use of CoolSculpting Elite and CoolSculpting Elite applicators for noninvasive subcutaneous fat reduction of the abdomen, flanks, upper arms, inner thighs, outer thighs, and submental area in healthy volunteers.

**Number of Participants:** Approximately 110 participants will be enrolled and approximately 96 participants are expected to complete the primary endpoint assessment based on an anticipated attrition rate of 12% or less.

The effectiveness measures are the CSQ for midsection (abdomen and flanks) and other treated body areas, the CGPQ, the CPIQ, Participant Evaluation of Noticeable Improvement, photography with IPR, and 3D Imaging.

The primary effectiveness endpoint is the proportion of participants who report being “satisfied” or “very satisfied” on item 1 for the CSQ-Midsection, measured at Week 12 (Visit 8) for participants who receive 1 treatment session, or at Week 20 (Visit 9) for participants who receive 2 treatment sessions.

**Intervention Groups and Duration:** All participants will be assigned a participant number sequentially based on the order in which the participant is screened into the study. This participant number will serve as the participant identification number on all study documents.

Participants are eligible to receive up to two treatment sessions separated 8 weeks apart for the body areas eligible for treatment. Assessments will be completed 12 weeks after the final treatment session.

- If a participant receives only one treatment session for specific body area(s), the participant will return at Visit 8 for the 12-week post-treatment session 1 follow-up assessment and study exit.
- If a participant receives two treatment sessions for specific body area(s), the participant will return at Visit 9 for the 12-week post-treatment session 2 follow-up assessment and study exit.
- If a participant receives only one treatment session to a specific body area and two treatment sessions to another specific body area, the participant will return for both 12-week follow-up visits: Visit 8 for the 12-week post-treatment session 1 assessment of the body area that received only one treatment session and Visit 9 for the 12-week post treatment session 2 assessment of the body area receiving two treatment sessions; Visit 9 will also be the study exit visit for this participant.

Participant body areas selected for treatment during the study must be treated during the first treatment visit (Visit 2) and no new body areas may be treated at Visit 6. Participants planning to receive only one treatment session to a specific body area must have this treatment in Visit 2 during the first treatment session. Per investigator discretion, body areas identified for treatment may be treated simultaneously or sequentially. If sequential or simultaneous treatment is performed, there will be no difference in other treatment activities. Skin preparation, pain assessment, treatment site assessment, and post-massage, etc. will be identical in either case.

The study duration is up to approximately 20 weeks and consists of up to 7 scheduled study visits and 2 phone follow-ups per participant:

- Visit 1 (screening, Days -7 to 1)
- Visit 2 (treatment session #1, Day 1 + 3 days)

Note: Treatment plan may be completed within a 7-day window from the day when the initial treatment is administered for this visit. The entire treatment session #1 plan for all the body areas selected for treatment must be completed within these 7 days.

- Visit 3 (1-week phone follow-up from last treatment day for participants who received treatment session #1 on any body area)

Note: If any of the following local effects of erythema, bruising, swelling, and/or sensory alteration are reported during Visit 3, additional phone follow-up (or in-person visit if aligned to planned study visit) will be scheduled in accordance with the time criteria outlined in Table 2-1 for potential AE categorization.

- Visit 4 (4-week follow-up after treatment session #1, Day 28 + 10 days)
- Visit 5 (8-week follow-up after treatment session #1, Day 56 + 14 days)
- Visit 6 (treatment session #2 [optional], Day 56 + 14 days, can be completed on the same day as Visit 5)

Note: Only body area(s) that were treated at Visit 2 and that require a second treatment session are to be treated at Visit 6. The treatment plan for specific body area(s) may be completed within a 7-day window from when the initial treatment is administered for this visit. The entire treatment session #2 plan for the body area(s) selected for a second treatment must be completed within these 7 days.

- Visit 7 (1-week phone follow-up from last treatment day for participants who received treatment session #2 on any body area)

Note: If any of the following local effects of erythema, bruising, swelling, and/or sensory alteration are reported during this Visit, additional phone follow-up (or in-person visit if aligned to planned study visit) will be scheduled in accordance with the time criteria outlined in Table 2-1 for potential AE categorization.

- Visit 8 (12-week follow-up/exit for participants with any body area that underwent only treatment session 1 at Visit 2, Day 84 + 14 days). If the participant receives only one treatment session to all body areas, this visit is also the study exit visit.

Note: If the participant receives only one treatment session to a specific body area and two treatment sessions to another specific body area, the body area that received only one treatment session will be assessed at this visit. The participant will return at Visit 9 for assessment of body area that received two treatment sessions and study exit.

[figure not shown]
- Visit 9 (20-week follow-up/exit, corresponding to 12-week follow up for participants with any body area that underwent treatment session 2 at Visit 6, Day 140 + 14 days). If the participant receives two treatment sessions to any or all treated body areas, this visit is also the study exit visit.

During the course of the study, should it ever become necessary to remain isolated at home or to shelter-in-place per local, regional, or state pandemic-related orders, the sponsor will engage with study site staff in efforts to ensure the safety of participants, maintain protocol compliance, and minimize risks to the integrity of the study while trying to best manage participant continuity of care. This may include alternative methods for assessments (eg, phone contacts or virtual site visits) in agreement with the sponsor. In all cases, these alternative measures must be allowed by local regulations and permitted by the Independent Review Board (IRB)/Independent Ethics Committee (IEC). Investigators should notify the sponsor if any urgent safety measures are taken to protect the participants against any immediate hazard.

## 1.2. Schema

The study schema is presented in Figure 1-1.

**Figure 1-1** Study Schema

The SoA is presented in Table 1-1. Study procedures are recommended to be done in sequence as listed in the below schedule.

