Treatment site assessment		X		X	X	X		X	X	Conduct after cryo-lipolysis treatments and prior to massage at Visits 2 and 6.
Height	X									
Weight	X	X		X	X			X	X	Conduct before cryo-lipolysis treatments at Visits 2 and 6.
2D/3D Photography 	X	X		X	X			X	X	See Section 8.1.2, conduct before cryo-lipolysis treatment at Visits 2 and 6
Cryolipolysis Treatment		X				X				See Section 6
Pain Assessment		X	X	X	X	X	X	X	X	See Section 8.2.1

- 1a Phone follow-up should be scheduled 7 days from last treatment visit day in instance where participant received treatment session #1 over multiple days.
- 1b If, during this phone follow-up, any of the following local effects of erythema, bruising, swelling, and/or sensory alteration are reported related to treatment session #1, additional phone follow-up (or in-person visit if aligned to planned study visit) will be scheduled in accordance with the time criteria outlined in Table 2-1 for potential AE categorization.
- 2a Phone follow-up should be scheduled 7 days from last treatment visit day in instance where participant received treatment session #2 over multiple days.
- 2b If, during this phone follow-up, any of the following local effects of erythema, bruising, swelling, and/or sensory alteration are reported related to treatment session #2, additional phone follow-up (or in-person visit if aligned to planned study visit) will be scheduled in accordance with the time criteria outlined in Table 2-1 for potential AE categorization.
-  If a participant receives only one treatment session for specific body area(s), the participant will return at Visit 8 for the 12-week post-treatment session #1 follow up assessment and study exit. If a participant receives two treatment sessions to any or all treated body areas, participant will return at Visit 9 for 12-week post-treatment session #2 follow-up and study exit. If a participant receives only one treatment session to one specific body area and two treatment sessions to another specific body area, the participant will return for Visit 8 for 12-week follow-up for the body area that received only one treatment session and Visit 9 for 12-week follow-up of body area that received two treatment sessions. The exit for this participant is Visit 9.
-  For select study sites with 3D camera system, 3D images will also be taken at this time.

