Note: Treatment plan may be completed within a 7-day window from the day when the initial treatment is administered for this visit. The entire treatment session #1 plan for all the body areas selected for treatment must be completed within these 7 days.

- Visit 3 (1-week phone follow-up from last treatment day for participants who received treatment session #1 on any body area)

Note: If any of the following local effects of erythema, bruising, swelling, and/or sensory alteration are reported during Visit 3, additional phone follow-up (or in-person visit if aligned to planned study visit) will be scheduled in accordance with the time criteria outlined in Table 2-1 for potential AE categorization.

- Visit 4 (4-week follow-up after treatment session #1, Day 28 + 10 days)
- Visit 5 (8-week follow-up after treatment session #1, Day 56 + 14 days)
- Visit 6 (treatment session #2 [optional], Day 56 + 14 days, can be completed on the same day as Visit 5)

Note: Only body area(s) that were treated at Visit 2 and that require a second treatment session are to be treated at Visit 6. The treatment plan for specific body area(s) may be completed within a 7-day window from when the initial treatment is administered for this visit. The entire treatment session #2 plan for the body area(s) selected for a second treatment must be completed within these 7 days.

- Visit 7 (1-week phone follow-up from last treatment day for participants who received treatment session #2 on any body area)

Note: If any of the following local effects of erythema, bruising, swelling, and/or sensory alteration are reported during this Visit, additional phone follow-up (or in-person visit if aligned to planned study visit) will be scheduled in accordance with the time criteria outlined in Table 2-1 for potential AE categorization.

- Visit 8 (12-week follow-up/exit for participants with any body area that underwent only treatment session 1 at Visit 2, Day 84 + 14 days). If the participant receives only one treatment session to all body areas, this visit is also the study exit visit.

Note: If the participant receives only one treatment session to a specific body area and two treatment sessions to another specific body area, the body area that received only one treatment session will be assessed at this visit. The participant will return at Visit 9 for assessment of body area that received two treatment sessions and study exit.

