Urine Pregnancy Test	X	X				X				See Protocol Section 8.2.3, conduct before cryo-lipolysis treatments at Visits 2 and 6. At Visits 2 and 6, repeat if participant is treated over multiple days with > 24 hours between treatments.
Treatment site assessment		X		X	X	X		X	X	Conduct after cryo-lipolysis

Evaluations	Visit 1 Screening	Visit 2 Treatment Session #1	Visit 3 1-week Phone Follow-up a,b	Visit 4 4-week Follow-up	Visit 5 8-week Follow-up	Visit 6 Treatment Session #2	Visit 7 1-week Phone Follow-up 2a,b	Visit 8 12-week Follow-up/Exit for participants who received only 1 treatment session 	Visit 9 20-week (12-week Follow-up/ Exit for participants who received 2 treatment sessions) 	Notes
										treatments and prior to massage at Visits 2 and 6.
Height	X									
Weight	X	X		X	X			X	X	Conduct before cryo-lipolysis treatments at Visits 2 and 6.
2D/3D Photography 	X	X		X	X			X	X	See Protocol Section 8.1.2, conduct before cryo-lipolysis treatment at Visits 2 and 6
Cryolipolysis Treatment		X				X				See Protocol Section 6
Pain Assessment		X	X	X	X	X	X	X	X	See Protocol Section 8.2.1
AE, SAE, ADE, SADE	X	X	X	X	X	X	X	X	X	At Visits 2 and 6, repeat if participant is treated over multiple days with > 24 hours between treatments.
Device Complaint Query		X	X	X	X	X	X	X	X	At Visits 2 and 6, repeat if participant is treated over multiple days with > 24 hours

Evaluations	Visit 1 Screening	Visit 2 Treatment Session #1	Visit 3 1-week Phone Follow-up 1a,b	Visit 4 4-week Follow-up	Visit 5 8-week Follow-up	Visit 6 Treatment Session #2	Visit 7 1-week Phone Follow-up 2a,b	Visit 8 12-week Follow-up/Exit for participants who received only 1 treatment session 	Visit 9 20-week (12-week Follow-up/ Exit for participants who received 2 treatment sessions) 	Notes
										between treatments.
CSQ [6 versions] 					X			X	X	See Protocol Section 10.6- 10.11
CGPQ 								X	X	See Protocol Section 10.12
CPIQ 		X			X			X	X	See Protocol Section 10.13 Complete before cryolipolysis treatment at Visit 2.
Participant Evaluation of Noticeable Improvement				X						See Protocol Section 10.15
								X	X	[REDACTED]

1a Phone follow-up should be scheduled 7 days from last treatment visit day in instance where participant received treatment session #1 over multiple days.

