#### 9.5.2

#### Main Analysis of Exploratory Efficacy Endpoints

- [REDACTED]
- [REDACTED]

[REDACTED]

In addition, two-sided 95% CI on mean change from baseline by visit will be calculated based on the paired t-test. P-value on change from baseline by visit will be provided based on the paired t-test.

The number and percentage of participants in each category for each item of CGPQ at Week 12 (Visit 8) for participants who receive 1 treatment session, or at Week 20 (Visit 9) for participants who receive 2 treatment sessions, or at 12 weeks +14 days post treatment session 2 for participants who had their treatment session 2 rescheduled because of the CoolSculpting® Elite treatment hold in the US on / after 24th August 2021 will be summarized for the Evaluable Population 1 and Evaluable Population 4.

The number and percentage of participants in each category of CSQ-Midsection Item 2 at Week 12 (Visit 8) for participants who receive 1 treatment session, or at Week 20 (Visit 9) for participants who receive 2 treatment sessions, or at 12 weeks +14 days post treatment session 2 for participants who had their treatment session 2 rescheduled because of the CoolSculpting® Elite treatment hold in the US on / after 24th August 2021 will be summarized for the Evaluable Population 1 and the two-sided Fisher's exact 95% CI on the percentage of participants with improvement (a lot of improvement, moderate improvement, and a little improvement) will be provided.

The number and percentage of participants reporting noticeable improvement in any treated body area, all treated body areas, and each treated body area at Week 4 (Visit 4) post treatment session 1 will be summarized for the Evaluable Population 1 (midsection) and Evaluable Population 2 (other treated body areas) and Evaluable Population 3 (any treated body area, all treated body areas) and the two-sided Fisher's exact 95% CI on the percentage will be provided.

For midsection, the descriptive statistics of the adjusted total volume of fat (cc) at baseline and post-baseline visits, [REDACTED]

[REDACTED]

For outer thigh (left, right, and combined left and right) and submental area, the descriptive statistics of the volume of fat (cc) change from baseline values will be provided for the Evaluable Population 2.

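### The recommended order of procedures puts the self-rated primary item after examination, weigh-in, photographs, pain scoring and the adverse event and complaint enquiries at Visits 8 and 9; the questionnaires should come first

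*Protocol*

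**What the plan says.** Protocol section 1.2 makes the schedule of activities a suggested running order as well as a list: "Study procedures are recommended to be done in sequence as listed in the below schedule".

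In the public copy, the protocol's own table can be read only as far as the "Pain Assessment" row, although its footnotes 5 to 7 show that questionnaire rows belong to it. The SAP reproduces the schedule in section 2.2, and there the order is visible. Treatment site assessment, height, weight, photography, cryolipolysis and pain come first. The rows "AE, SAE, ADE, SADE" and "Device Complaint Query" follow, and only then CSQ, CGPQ and CPIQ.

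The primary endpoint (Protocol 9.4.2, SAP 3.1) is the proportion satisfied or very satisfied on CSQ-Midsection Item 1, at Visit 8 after one session or Visit 9 after two.

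One visible note fixes the timing of a questionnaire within a visit. It is in the CPIQ row: "See Protocol Section 10.13 Complete before cryolipolysis treatment at Visit 2". Protocol 8.1.1 says that the questionnaires are on paper, but not when in the visit they are completed. Protocol 4.1 says of Visit 6 that it "can be completed on the same day as Visit 5".

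**The concern.** The primary outcome is one self-rated item in a single-arm, open-label study. Before answering it, a participant whose site follows the listed order has been examined, weighed, photographed, asked to score pain and asked about adverse events and device complaints. Each contact could colour the answer. A complaint enquiry might lower a rating, while a favourable weigh-in or staff attention might raise it, and the effect could differ between sites.

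A randomised comparison would share such an effect between arms and largely cancel it in the difference. Here the observed rate is itself the result, so any shift passes straight into the estimate. SAP 9.3.3 plans no sensitivity analysis of the primary endpoint. What is at stake is the credibility of the headline satisfaction rate. No test decision is involved, because the plan has no hypothesis.

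**Working it through.** **Step 1: which procedures share a visit with the questionnaires.** Rows are in listed order, with marks taken from the SAP's schedule (height is at screening only):

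| Row | V2 | V5 | V6 | V8 | V9 |
|---|---|---|---|---|---|
| Treatment site assessment | X | X | X | X | X |
| Weight | X | X | | X | X |
| Photography | X | X | | X | X |
| Cryolipolysis | X | | X | | |
| Pain | X | X | X | X | X |
| Adverse events | X | X | X | X | X |
| Device complaint query | X | X | X | X | X |
| CSQ | | X | | X | X |
| CGPQ | | | | X | X |
| CPIQ | X | X | | X | X |

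Read down columns V8 and V9. Six marked rows in the table precede the CSQ: site assessment, weight, photography, pain, adverse events and device complaints. Cryolipolysis is not marked in either column.

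**Step 2: is there an instruction that overrides this order for the CSQ?** The Notes column does override row order in places. Site assessment is listed above cryolipolysis, but its note places it after treatment and before massage at Visits 2 and 6. The CPIQ note places the baseline CPIQ before treatment at Visit 2. The CSQ row only points to the appendices that hold the questionnaires. No visible text puts the CSQ ahead of the other procedures at Visits 8 and 9.

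**Step 3: the combined Visit 5/6 day.** CSQ and CPIQ are marked under Visit 5 and cryolipolysis under Visit 6. A site that finishes one column before starting the next completes the questionnaires before treatment. A site that merges the two columns and works down the rows completes them after it. The weight and photography rows are likewise marked at Visit 5 and not at Visit 6, yet their notes require them before treatment at Visits 2 and 6. CSQ and CPIQ have no matching note for that day.

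**Step 4: the plan's own figure.** Protocol 9.2 gives n = 96, rate p = 0.639, a two-sided exact 95% interval of width 0.2, and 12% attrition. The Clopper-Pearson limits, with x = p × n, are:

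- lower = Beta quantile at 0.025 with parameters x and n − x + 1
- upper = Beta quantile at 0.975 with parameters x + 1 and n − x

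At n = 96, x = 0.639 × 96 = 61.344. The limits are 0.5346 and 0.7346, a width of 0.19996. At n = 95 the width is 0.2010, so 96 is the smallest n that meets the target. Enrolment is 96 / (1 − 0.12) = 109.1, rounded up to 110. The plan's figures reproduce, and changing the order of procedures leaves them untouched.

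**Step 5: what a shift would look like.** One rating in 96 that crosses the satisfied boundary changes the rate by 1/96 = 1.04 percentage points. This restates the denominator and is not evidence of an effect. The documents give no order effect, so the shifts below are assumptions:

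| Assumed shift (points) | Rate | Exact 95% interval | Width |
|---|---|---|---|
| −10 | 0.539 | 0.434 to 0.641 | 0.207 |
| −5 | 0.589 | 0.484 to 0.688 | 0.205 |
| 0 | 0.639 | 0.535 to 0.735 | 0.200 |
| +5 | 0.689 | 0.586 to 0.780 | 0.193 |
| +10 | 0.739 | 0.639 to 0.823 | 0.184 |

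The width stays between about 0.18 and 0.21. An interval can meet its precision target while centred in the wrong place, so the planned precision gives no warning.

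**The case against.** The strongest reply is that nothing here is broken. Section 1.2 recommends an order and does not require it, and the site assessment note shows that the table is not a strict sequence. The sequence sentence is in the protocol, while the questionnaire rows are visible only in the SAP, which gives no sequence instruction of its own. The questionnaires are redacted, so instructions on the forms cannot be seen. Protocol 8.3.2 prefers open-ended, non-leading questions about adverse events. No text says that participants learn their weight or see their photographs before answering. The study is descriptive, and no bias has been demonstrated.

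All of this limits the strength of the point, but it does not supply the missing instruction. The exceptions in the Notes column show that the authors write down a departure from row order when they want one, and none is visible for the CSQ.

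Two stronger readings are tempting, and the documents support neither.

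- A reader might infer that treatment precedes the primary rating, because cryolipolysis is listed above the CSQ. It does not: treatment is marked only at Visits 2 and 6.
- A reader might infer that the plan schedules the Week 8 CPIQ after the second cooling session. The two are in different visit columns, so this arises only if a site merges them on a combined day. A footnote to the SAP schedule further limits the same-day option to participants whose second session came before the US treatment hold. The Week 8 CSQ is neither a primary nor a secondary endpoint, and CPIQ is exploratory. SAP 9.5.2 does say that a "two-sided 95% CI on mean change from baseline by visit will be calculated based on the paired t-test", but the text before it is redacted, so its link to CPIQ is an inference.

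**Conclusion.** The point stands as a low-cost improvement to a design choice; it does not identify a contradiction or an error. At Visits 8 and 9 the recommended order places the only primary item after six kinds of staff contact, and no visible text puts it first. It applies to every primary rating, about 96 by the plan's expectation. The size and direction of any effect are unknown and cannot be derived from the documents. The 1.04 points per rating and the assumed shifts of 5 and 10 points show scale only.

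The conclusion rests on two assumptions: that the protocol's own table lists the questionnaire rows in the same order as the SAP's copy, and that no redacted text tells participants to complete the CSQ before the other procedures. The Visit 5/6 matter is a minor clarification and does not touch the primary endpoint.

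**What to change.** 1. In the protocol's schedule of activities and the SAP's copy, move the CSQ, CGPQ and CPIQ rows above treatment site assessment, weight, photography, pain, adverse events and device complaints. The noticeable-improvement question at Visit 4 can move with them.
2. Add to Protocol 8.1.1: At each visit where questionnaires are due, participants complete them before treatment site assessment, weight, photography, pain scoring, adverse event enquiry and device complaint enquiry.
3. As a minor clarification, extend the CPIQ timing note so that, when Visits 5 and 6 fall on the same day, the Visit 5 CSQ and CPIQ are completed before cryolipolysis. This matches the notes already given for weight and photography.

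The cost is a few table rows, one sentence and one note. Sample size, endpoint, interval method, visits and staffing are unchanged. The only downside is a small change to site workflow.
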